8.6 Molecular Analyses

The molecular analyses will be performed on the evaluable population. Descriptive statistics will be used to compare the pre-and post molecular findings.

A correlation analysis between the molecular alterations from the baseline tumor samples and the sample collected following administration of darolutamide, during the definitive BC surgery/pre-NAST biopsy will be conducted.

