Modulation of AR signaling, either inhibitory or stimulatory, has previously been explored in BC with somewhat contrasting results. Androgen therapy has historically been used but largely abandoned in the 1970s due to its toxicity and the emergence of ER-directed therapies.

More recently, clinical reports of AR antagonism have been promising, especially in TNBC. Bicalutamide has been assessed in a phase II, single-arm trial in AR+, ER- advanced BC, and showed clinical benefit rate of 19% with a good safety profile.¹⁰ Some newer drugs like enzalutamide, have also been tested in TNBC. A phase II study in AR+ TNBC proved that this therapy was well-tolerated and showed promising clinical activity in selected patients.¹¹

These developments in combination with an improved understanding of AR signaling in different BC subtypes led to the renewed interest in targeting AR. However, the value of AR antagonists in the management of BC, the molecular alterations that occur after exposure to these agents and whether there are biomarkers useful to predict their effectiveness, still need to be fully elucidated. Increased understanding of AR blockade and its potential value in different BC subtypes and clinical testing of newer and more potent AR antagonists like darolutamide, is thus timely and necessary.

Translational Oncology Research Laboratories (TORL, at University of California Los Angeles, US) has conducted cell viability studies in 49 BC cell lines exposed to different concentrations of darolutamide. The studies have shown that cell lines belonging to each of the three BC subtypes (HR+, HER2+, TN) responded different to darolutamide. Responses are mainly seen in cell lines expressing AR but also in some lines that lack AR expression, suggesting that AR expression may not be the only biomarker predicting response to darolutamide (unpublished).

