The current study will enroll EBC female patients with differing BC subtypes, with the intent of characterizing the molecular alterations in BC tissue before and after short-term exposure to the antiandrogen darolutamide. Studying the biological mechanisms in which darolutamide targets the AR in BC will be crucial in understanding its potential role in this disease, as well as providing the foundation for the rational development of darolutamide in the disease. Such information may suggest that darolutamide be combined with other modalities; for example, if treatment with the drug is discovered to affect multiple signaling pathways. Molecular profiling of tumor samples before and after darolutamide treatment may permit the identification of patients likely or unlikely to respond to the agent based on the biological and molecular characteristics of their tumors. Since it is essential to evaluate the molecular effects of darolutamide in tumors not previously exposed to chemotherapy or radiation, patients with untreated primary breast tumors amenable to a pre-

treatment biopsy followed by a post-darolutamide sample at definitive surgery or prior to starting neoadjuvant systemic therapy (NAST) represent an ideal population to study. Male patients will not be enrolled due to pathological and biological differences in male breast cancer.¹²

Although no direct benefit from the treatment with darolutamide is expected in the participating patients, the good tolerability and favourable safety profile of darolutamide at the selected dose, the proposed brief duration of treatment, and the fact that patients enrolled in the study will not be required to undergo any delay in definitive surgery or start of NAST if indicated, should ensure the safety and ethical set-up of the trial.

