6.5.7 Tumor Tissue Collection and Molecular Evaluation

All tumor samples will be submitted to the study Central Laboratory and will be stored for up to 20 years, unless otherwise required per local regulations, Investigator, IRB/IEC and/or the patient.

Full details on the analyses to be performed on the biologic samples and procedures for sample collection, labeling, storage and shipment/return of biological samples will be described in separate document(s) (e.g. Laboratory Manual, Samples Plan).

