6.5.7.2 Molecular Evaluation

The primary endpoint of the study is to explore and define the molecular alterations that may occur following darolutamide administration through comparisons of BC tissue before and after short-term exposure to darolutamide.

At least, the following markers will be assessed on the collected samples. In all experiments, appropriate positive and negative controls will be included.

- AR
- ER
- PgR
- HER2
- ki67
- Cytokeratins 5 and 6

Tissue microarrays will be developed from all tumor specimens. Other *in situ* assays for activated downstream signaling molecules will be performed using tissue sections and/or tissue microarrays. Promising candidate genes obtained from the microarray analysis will be validated using the frozen

tissue arrays generated above and using appropriate probes (i.e. antibodies, if available, or nucleic acid probes).

Additional assays in example but not limited to Reverse Phase Protein Analysis (RPPA), sequenciation of the RNA, immunohistochemistry (IHC) etc. may be performed based on the molecular analysis finding and/or in the future as new technology and data become available.

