8.5 Sample Size

The primary objective of this trial is to evaluate molecular alterations occurring in BC tissue following short-term darolutamide administration.

Up to 60 patients (minimum of 8 but up to 20 patients in each BC subtype: triple-negative, HR+/HER2 negative, HER2 positive) will be required for the performance of the molecular studies and possible hypothesis generation.

A patient will be considered evaluable if the following criteria are met:

- Minimum duration of treatment with darolutamide is of 14 days, with a minimum of 10 consecutive days of treatment prior to the definitive BC surgery/pre-NAST biopsy.
- Mandatory tumor tissue is collected at screening and at BC surgery/pre-NAST biopsy according to the protocol and submitted to the central laboratory.
- Adequacy for molecular assessment of the tumor tissue collected before and after the protocol treatment initiation. The adequacy will be evaluated by the central laboratory.

Assessment of patient evaliability, safety and distribution of patients with respect to hormone receptor status and HER2 status will be performed by the SSC at given time points depending on the recruitment, for example once 20, around 35 and once all patients have been enrolled and undergone the EoS per protocol. This will allow SSC to ascertain that the appropriate number of evaluable patients is being accrued, that more or less patients may be required, or in the extreme case, that accrual should close if the patient evaliability rate is very low and/or safety concerns arise.

The SSC will define the evaliability of patients that discontinue treatment more than 3 days before BC surgery/pre-NAST biopsy; molecular analyses may be taken into consideration for the decision about the evaliability of such patients.

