|---|----|
| 3.5.6. Death..... | 12 |
| 4. List of Planned Statistical Outputs | 12 |
| 4.1. Planned Tables..... | 12 |
| 4.2. Planned Listings..... | 14 |
| 4.3. Planned Graphs..... | 16 |
| 5. Appendix | 16 |
| 5.1. Protocol Synopsis – Protocol v3.0..... | 16 |
| 5.2. Protocol Synopsis – Protocol v5.0 (Germany)..... | 22 |

List of Abbreviations

| | |
|--------|--|
| ADSL | Subject-Level Analysis Dataset |
| ADaM | Analysis Data Model |
| AE | Adverse Events |
| CM | Concomitant Medications |
| CTCAE | Common Terminology Criteria for Adverse Events |
| EBC | Early Breast Cancer |
| EoS | End of Study |
| ITT | Intent-to-treat or Intention-to-treat |
| ITTF | Intent-to-treat Population Flag |
| MedDRA | Medical Dictionary for Regulatory Activities |
| NCI | National Cancer Institute |
| PT | Preferred Term |
| Q1 | First Quartile |
| Q3 | Third Quartile |
| RDI | Relative Dose Intensity |
| SAE | Serious Adverse Event |
| SAFF | Safety Population Flag |
| SAP | Statistical Analysis Plan |
| SAS® | Statistical Analysis System Software |
| SOC | System Organ Class |
| SSC | Study Steering Committee |
| TEAE | Treatment Emergent Adverse Event |
| TRIO | Translational Research in Oncology |
| WHODD | World Health Organization Drug Dictionary |

1. Introduction

This Statistical Analysis Plan (SAP) describes the detailed statistical methodology for executing the statistical analyses of the Secondary Objective according to TRIO030 protocol version 3.0 and version 5.0 (Germany).

Statistical analysis will be performed by TRIO using SAS® software Version 9.4 or higher.

2. Study Design and Objectives

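### Does Protocol 8.6 need a named change measure, an interval and a defined correlation for the pre/post molecular comparison?

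*Protocol*

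**What the plan says.** Protocol 6.5.7.2 makes the primary endpoint the molecular alterations found "through comparisons of BC tissue before and after short-term exposure to darolutamide". It lists at least six markers: AR, ER, PgR, HER2, ki67, and cytokeratins 5 and 6 as one item.

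Protocol 8.6 restricts the molecular analyses to the evaluable population and gives two sentences of method. The first is "Descriptive statistics will be used to compare the pre-and post molecular findings". The second announces "A correlation analysis between the molecular alterations from the baseline tumor samples and the sample collected following administration of darolutamide", the later sample being the one taken at surgery or at the biopsy before neoadjuvant therapy.

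Evaluability under Protocol 8.5 requires tissue from both time points, and the central laboratory must confirm "Adequacy for molecular assessment of the tumor tissue collected before and after the protocol treatment initiation".

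The SAP does not cover this endpoint. Its Introduction limits it to "the detailed statistical methodology for executing the statistical analyses of the Secondary Objective", and SAP 3.1.3 leaves the molecular analyses to a separate document. Protocol 6.5.7 likewise assigns "Full details on the analyses to be performed on the biologic samples" to separate documents. Protocol 8.5 and SAP 2.3 and 3.1.3 all describe the purpose as possible hypothesis generation, and SAP 2.3 says cohort sizes did not come from a formal calculation.

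**The concern.** A before/after endpoint calls for the direction and size of the within-patient change and a measure of its uncertainty. Section 8.6 promises none of these by name. The only specific technique it mentions is a correlation with no stated variables, coefficient or purpose.

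Two natural readings would not answer the question. A marker's pre value against its own post value does not register a shift common to all patients. A marker's baseline against its own change is negative even when nothing happens, through regression to the mean. If either were reported as evidence of alteration, markers could be taken forward or dropped for the wrong reason, in cohorts of 7, 10 and 19 patients where a bare point estimate hides a lot of uncertainty.

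**Working it through.** **The plan's own figures.** Three subtypes of up to 20 give 3 × 20 = 60, as Protocol 8.5 states. Enrolment in SAP 2.3 is 7 + 19 + 10 = 36. No power or precision figure is stated, so there is none to reproduce.

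**What a same-marker correlation can show.** Assumed, not in the documents: pre = t + e1 and post = t + shift + e2, with SD(t) = 1 and noise SD s = 0.7 (range 0.4 to 1.0).

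- No effect, or the same shift in everyone: r = 1/(1 + s²) = 1/1.49 = 0.67 (0.86 to 0.50).
- A 2-SD fall in a random half (variance of shift = 1): r = 1/√((1 + s²)(2 + s²)) = 1/√(1.49 × 2.49) = 0.52. A 2-SD rise in a random half gives the same value. So does no effect with s = √(1/0.519 − 1) = 0.96.
- Baseline against change, no effect: r = −s²/√((1 + s²) × 2s²) = −0.49/√(1.49 × 0.98) = −0.41 (−0.26 to −0.50).

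The criticism of these two readings is therefore correct. Two points limit it. Section 8.6 adopts neither reading as a test of change. A third reading, baseline of one marker against change in another, suits the aim in Protocol 1.3.1 that profiling "may permit the identification of patients likely or unlikely to respond to the agent"; its null correlation is 0 if noise is independent between markers, and about 0.5 × (−0.41) = −0.20 if their noise correlates 0.5.

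**What the same-marker r adds.** Beside ordinary pre and post summaries on the same scale, a Pearson r supplies the SD of the change: SD² = SDpre² + SDpost² − 2 × r × SDpre × SDpost. In the model this is 2 × 1.49 × (1 − 0.671) = 0.98, which equals 2s². Pre and post means and SDs with r are thus enough to form the paired interval.

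**Precision of the within-patient change.** The half-width of the 95% interval for a mean change, in SDs of change, is t(0.975, n−1)/√n. No noise assumption is needed.

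| n | Half-width |
|---|---|
| 7 | 0.92 |
| 10 | 0.72 |
| 19 | 0.48 |
| 36 (pooled) | 0.34 |

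These are best cases, since evaluable and centrally classified numbers may be smaller (1.05 at n = 6, 1.24 at n = 5).

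**What prescribing intervals would bring.**

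- Number: six markers in three subtypes is 18 intervals, with 18 × 0.05 = 0.9 expected to exclude zero under no change. Adding the overall group gives 6 × 4 = 24, with 24 × 0.05 = 1.2 expected. The simulated chance of at least one among the 24 is 66% with independent markers and 34% with marker correlation 0.9.
- Regression to the mean in the change itself: ER, PgR and HER2 define the subtypes (Protocol 6.1.2.2). If subtype is fixed on the pre-treatment sample (an assumption), grouping selects on baseline. With s = 0.7 and no effect, the expected change is s²/(1 + s²) = 0.329 times the distance of the group's mean baseline from the overall mean. For the lowest 20% that is 0.329 × 1.40 × 1.22 = 0.56, or 0.61 within-group SDs of change (0.92). For the lower half it is 0.329 × 0.80 × 1.22 = 0.32, or 0.34 SDs (0.94).
- Median intervals: at n = 5 the widest sign-based interval covers 1 − 2 × 0.5⁵ = 93.75%, so a distribution-free 95% interval does not exist. At n = 7 it is the minimum to the maximum (98.4%), which a descriptive table normally shows.

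**The case for a change.** The strongest case for acting is that this is the primary endpoint and the two sentences in 8.6 are all the statistical method the supplied documents give for it. Protocol 9.1 has the steering committee analyse according to the statistical plan, yet the SAP excludes this objective. The examples of separate documents in Protocol 6.5.7 are a laboratory manual and a samples plan, neither of them obviously an analysis plan. Protocol 1.3.1 reports that "cell lines belonging to each of the three BC subtypes (HR+, HER2+, TN) responded different to darolutamide", so effects may well differ between patients, and a correlation would then move without showing which way. An exploratory study still needs direction, size and uncertainty to choose markers, and the remedy is only wording and a few tables.

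The factual part stands: 8.6 is brief, does not define the correlation, and does not point to the separate document. It also stands that a same-marker correlation should not be offered as evidence of change.

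The step from there to a defect does not. SAP 3.1.3 refers specifically to a separate document on the molecular analyses, and that document may already set out a paired analysis. The misuse of the correlation is a possible reading, not something 8.6 says. The cost is also more than wording: two protocol versions (v3.0 and v5.0 Germany) would be edited after enrolment closed on 14 February 2019, and Protocol 9.4 might require formal amendment.

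**Conclusion.** No change follows. This is missing detail that the plan defers elsewhere, and a competent analyst with two samples per patient would fill it sensibly. The descriptive pre/post comparison already matches the endpoint, pairing is built into evaluability, and the hypothesis-generating status is stated in three places. No figure is wrong, and no stated rule would produce a wrong result.

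Reporting within-patient change with its uncertainty is good practice, but for the triple-negative cohort it yields an interval of about ±0.92 SDs of change at best. A blanket requirement by subtype would add 24 intervals and, for ER, PgR and HER2, a possible bias of roughly 0.3 to 0.6 SDs of change.

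The correlation and bias figures rest on the assumed model and noise SD; the half-widths and interval counts do not. The conclusion assumes that the separate molecular document exists or will be written before analysis, and that the correlation is not presented as proof of alteration. Without an untreated control, no choice of summary would separate a drug effect from other differences between the two samples.

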9. ADMINISTRATIVE, ETHICAL AND REGULATORY STANDARDS

9.1 Steering Committee

The SSC of the trial will be composed of the study Chair(s) and representatives from TRIO. The SSC will include also a number of study principal Investigators. Other members may be added after consultation with the SSC members. The SSC will be constituted prior to the enrollment of the first patient.

The SSC will have the sole responsibility for the scientific conduct and integrity of the trial. Responsibilities include development and approval of the protocol document, monitoring of accrual, compliance and safety during the conduct of the trial. The SSC will be solely responsible for the analysis, interpretation and public disclosure of the results of the trial in accordance with the statistical plan. The SSC should endeavor to ensure that the study is conducted at all times to the standards set out in Guidelines for Good Clinical Practice (GCP). In all of the deliberations of the SSC, the rights, safety and well being of the study participants are the most important considerations.

9.2 Ethical Conduct of the Study

This clinical study was designed and shall be implemented and reported in accordance with the clinical trial protocol, the ICH Harmonized Tripartite Guidelines for Good Clinical Practice, applicable local regulations (including European Directives 2001/20/EC and 2005/28/EC and the US Code of Federal Regulations Title 21), the Council for International Organizations of Medical Sciences (CIOMS), and the ethical principles laid down in the Declaration of Helsinki. This study will be conducted under ethical, scientific and medical standards that protect the rights and welfare of participants.

9.3 Institutional Review Board/Independent Ethics Committee (IRB/IEC)

Each participating institution must provide for the review and approval of this protocol and the associated informed consent documents and recruitment material by an appropriate IEC or IRB. The IEC/IRB decision concerning the conduct of the study will be made in writing and kept with the Investigator study file. A copy of this decision will also be provided to TRIO.

Particular attention is drawn to the Food and Drug Administration (FDA's requirements for IRBs under 21 CFR Part 56). By signing the "Statement of Investigator" form (Form FDA 1572), the Investigator provides TRIO with the necessary assurance that an IRB is responsible for the initial/continuing review and subsequent approval of the proposed clinical study in accordance with these regulations when applicable.

The Investigator will agree to make required progress reports to the IEC/IRB, as well as report any SAEs, life-threatening problems or deaths if applicable per local regulations. The IEC/IRB will be informed of SAEs in other clinical studies conducted with the study drug by the Investigator or the Sponsor according to the local regulations. The IEC/IRB must be informed by the Investigator of the termination of the study.

9.4 Compliance with the Protocol and Protocol Amendments

Investigators ascertain they will apply due diligence to avoid protocol deviations. Under no circumstances should the Investigator contact TRIO or its agents monitoring the trial, if any, to request approval of a protocol deviation, as no such authorized deviations are permitted.

If the Investigator feels a protocol deviation would improve the conduct of the study this must be considered a protocol amendment, and unless such an amendment is agreed upon by TRIO and approved by the IRB/IEC it cannot be implemented. All significant protocol deviations will be recorded and reported in the Clinical Study Report (CSR).

Any modifications to the protocol which may impact on the conduct of the study, potential benefit of the patient or may affect patient safety, including changes of study objectives, study design, patient population, sample sizes, study procedures, or significant administrative aspects will require a formal amendment to the protocol. Such amendment will be agreed upon by TRIO, and approved by the Ethics Committee/IRB and Health Authorities where required, prior to implementation. Only amendments that are required to eliminate an immediate hazard to patients for patient safety can

be implemented prior to IRB/IEC approval. Notwithstanding the need for approval of formal protocol amendments, the Investigator is expected to take any immediate action required for the safety of any patient included in this study, even if this action represents a deviation from the protocol. In such cases, TRIO should be notified of this action and the IRB/IEC at the study site should be informed.

9.5 Monitoring, Auditing and Inspecting

TRIO or its representatives must be allowed to visit all study site locations periodically to assess the data, quality, and study integrity. On site, they will notably review study records and directly compare them with source documents, review regulatory documents, discuss the conduct of the study with the Investigator, verify study drug accountability, and verify that the facilities remain acceptable.

9.6 Recording, Processing and Retention of Data

The Investigator is responsible for the preparation and maintenance of adequate case histories designed to record all observations and other relevant data. All patient data reported on the eCRF must be derived from source documents and as such be consistent with the source documents, or the discrepancies must be explained.

Data will be entered and collected via an electronic data capture system using eCRFs. RDC is a validated system designed for entry of data in a way that is attributable, secure, and accurate, in compliance with U.S. FDA regulations for electronic records (21 CFR Part 11). Study site staff will receive training and have access to a manual for appropriate eCRF completion. All eCRFs should be completed by designated, trained site staff. eCRFs should be reviewed and electronically signed and dated by the Investigator or authorized designee. Only identified and trained users may view the data as their actions become part of the audit trial.

While study sites will be responsible for data entry, TRIO will be responsible for data management of this study, including quality checks.

The eCRF must be completed within 7 calendar days of data availability. All requested information must be entered on the eCRF. If an item is not available or is not applicable, it must be documented as such. The completed eCRF must be reviewed and approved by the Investigator or authorized designee. In the event of discrepant data, TRIO will request data clarification from the sites. The sites will resolve the discrepancy electronically in the RDC system. eCRF and data clarification documentation will be maintained in the RDC system's audit trail.

At the end of the study, the Investigator will receive patient data, for their site, in a readable format on CD, DVD, or other similar storage format that must be kept with the study records. Acknowledgement of receipt of the storage disc or similar is required.

The Investigator should retain the study documentation according to ICH-GCP, local regulations or as indicated in the contractual agreement whichever is longer.

